14.3.2 Listing of Deaths, Other Serious and Significant Adverse Events. Safety Analysis Set

Programming note:

Create an empty table with the following reference message: "Please refer to listing 16.2.7.1.3"

CureVac AG
CV-7202-104

Statistical Analysis Plan
24 February 2022

Sponsor Clinical Study Report
Protocol number Page x of y
14.3.3 Narratives of Deaths, Other Serious and Certain Other Significant Adverse Events, Safety Analysis Set

Programming note:
This is a cross-reference to section 12.3.2 of the CSR

CureVac AG
CV-7202-104

Statistical Analysis Plan
24 February 2022

Sponsor
Protocol number

Clinical Study Report
Page x of y

14.3.4 Abnormal Laboratory Value Listing (Each Subject), Safety Analysis Set

*Programming note:
Layout analogous to section 16.2 lab listings*

Sponsor
Protocol number

Clinical Study Report
Page x of y

14.3.5.1 Vaccination Site Reactogenicity Investigator Assessment Overview, Safety Analysis Set

Category [n (%)]	CV7202 1 µg (N = xx)	CV7202 2 µg (N = xx)	CV7202 5 µg (N = xx)	Rabipur (N = xx)
Any symptom with grade > 0	V3 (Day 1) V4 (Day 2/3) V5 (Day 8) V6 (Day 10) V8 (Day 29) V9 (Day 30)	xx (xx.x%) xx (xx.x%) xx (xx.x%) xx (xx.x%) xx (xx.x%) xx (xx.x%)	xx (xx.x%) xx (xx.x%) xx (xx.x%) xx (xx.x%) xx (xx.x%)	xx (xx.x%) xx (xx.x%) xx (xx.x%) xx (xx.x%) xx (xx.x%)

PROGRAM SOURCE: tlf-###, DATA CUT OFF DATE: DDMMYYYY

RUN DATE: DDMMYYYY hh:mm

CureVac AG
CV-7202-104

Statistical Analysis Plan
24 February 2022

Sponsor

Clinical Study Report

Page x of y

Protocol number

14.3.5.2 Vaccination Site Reactogenicity Investigator Assessment Overview by Treatment Group, Safety Analysis Set

Category [n (%)]	CV7202 1x1 µg (N = xx)	CV7202 2x1 µg (N = xx)	CV7202 1x2 µg (N = xx)	CV7202 2x2 µg (N = xx)
Any symptoms with grade > 0	V3 (Day 1) xx (xx.x%)	xx (xx.x%)	xx (xx.x%)	xx (xx.x%)
	V4 (Day 2/3) xx (xx.x%)	xx (xx.x%)	xx (xx.x%)	xx (xx.x%)
	V8 (Day 29)		xx (xx.x%)	xx (xx.x%)
	V9 (Day 30)		xx (xx.x%)	xx (xx.x%)

PROGRAM SOURCE: tlf-###, DATA CUT OFF DATE: DDMMYYYY

RUN DATE: DDMMYYYY hh:mm

CONFIDENTIAL

CV-7202-104_Statistical_Analysis_Plan_V1.0.docm

Sponsor
Protocol number

Clinical Study Report
Page x of y

14.3.5.3 Vaccination Site Reactogenicity Investigator Assessment, Safety Analysis Set

		CV7202 1 µg (N = xx)	CV7202 2 µg (N = xx)	CV7202 5 µg (N = xx)	Rabipur (N = xx)
Category [n (%)]					
Injection pain	V3 (Day 1)	Grade 0 xx (xx.x%) Grade 1 xx (xx.x%) Grade 2 xx (xx.x%) Grade 3 xx (xx.x%)	xx (xx.x%) xx (xx.x%) xx (xx.x%) xx (xx.x%)	xx (xx.x%) xx (xx.x%) xx (xx.x%) xx (xx.x%)	xx (xx.x%) xx (xx.x%) xx (xx.x%) xx (xx.x%)
	V4 (Day 2/3)	Grade 0 xx (xx.x%) Grade 1 xx (xx.x%) Grade 2 xx (xx.x%) Grade 3 xx (xx.x%)	xx (xx.x%) xx (xx.x%) xx (xx.x%) xx (xx.x%)	xx (xx.x%) xx (xx.x%) xx (xx.x%) xx (xx.x%)	xx (xx.x%) xx (xx.x%) xx (xx.x%) xx (xx.x%)
	V5 (Day 8)	Grade 0 xx (xx.x%) Grade 1 xx (xx.x%) Grade 2 xx (xx.x%) Grade 3 xx (xx.x%)			xx (xx.x%) xx (xx.x%) xx (xx.x%) xx (xx.x%)
	V6 (Day 10)	Grade 0 xx (xx.x%) Grade 1 xx (xx.x%) Grade 2 xx (xx.x%) Grade 3 xx (xx.x%)			xx (xx.x%) xx (xx.x%) xx (xx.x%) xx (xx.x%)
	V8 (Day 29)	Grade 0 xx (xx.x%) Grade 1 xx (xx.x%) Grade 2 xx (xx.x%) Grade 3 xx (xx.x%)	xx (xx.x%) xx (xx.x%) xx (xx.x%) xx (xx.x%)	xx (xx.x%) xx (xx.x%) xx (xx.x%) xx (xx.x%)	xx (xx.x%) xx (xx.x%) xx (xx.x%) xx (xx.x%)
	V9 (Day 30)	Grade 0 xx (xx.x%) Grade 1 xx (xx.x%) Grade 2 xx (xx.x%) Grade 3 xx (xx.x%)	xx (xx.x%) xx (xx.x%) xx (xx.x%) xx (xx.x%)	xx (xx.x%) xx (xx.x%) xx (xx.x%) xx (xx.x%)	xx (xx.x%) xx (xx.x%) xx (xx.x%) xx (xx.x%)

PROGRAM SOURCE: tlf-###, DATA CUT OFF DATE: DDMMYYYY

RUN DATE: DDMMYYYY hh:mm

Programming note:

CONFIDENTIAL

CV-7202-104_Statistical_Analysis_Plan_V1.0.docm

Repeat for redness, swelling, itching.

Sponsor

Clinical Study Report

Protocol number

Page x of y

14.3.5.4 Vaccination Site Reactogenicity Investigator Assessment by Treatment Group, Safety Analysis Set

Category [n (%)]	CV7202 1x1 µg (N = xx)	CV7202 2x1 µg (N = xxx)	CV7202 1x2 µg (N = xx)	CV7202 2x2 µg (N = xx)
Injection pain				
V3 (Day 1)	Grade 0 xx (xx.x%) Grade 1 xx (xx.x%) Grade 2 xx (xx.x%) Grade 3 xx (xx.x%)	xx (xx.x%) xx (xx.x%) xx (xx.x%) xx (xx.x%)	xx (xx.x%) xx (xx.x%) xx (xx.x%) xx (xx.x%)	xx (xx.x%) xx (xx.x%) xx (xx.x%) xx (xx.x%)
V4 (Day 2/3)	Grade 0 xx (xx.x%) Grade 1 xx (xx.x%) Grade 2 xx (xx.x%) Grade 3 xx (xx.x%)	xx (xx.x%) xx (xx.x%) xx (xx.x%) xx (xx.x%)	xx (xx.x%) xx (xx.x%) xx (xx.x%) xx (xx.x%)	xx (xx.x%) xx (xx.x%) xx (xx.x%) xx (xx.x%)
V8 (Day 29)	Grade 0 xx (xx.x%) Grade 1 xx (xx.x%) Grade 2 xx (xx.x%) Grade 3 xx (xx.x%)		xx (xx.x%) xx (xx.x%) xx (xx.x%) xx (xx.x%)	xx (xx.x%) xx (xx.x%) xx (xx.x%) xx (xx.x%)
V9 (Day 30)	Grade 0 xx (xx.x%) Grade 1 xx (xx.x%) Grade 2 xx (xx.x%) Grade 3 xx (xx.x%)		xx (xx.x%) xx (xx.x%) xx (xx.x%) xx (xx.x%)	xx (xx.x%) xx (xx.x%) xx (xx.x%) xx (xx.x%)

PROGRAM SOURCE: tlif-###, DATA CUT OFF DATE: DDMMYYYY

RUN DATE: DDMMYYYY hh:mm

Programming note:

Repeat for redness, swelling, itching.

CureVac AG
CV-7202-104

Statistical Analysis Plan
24 February 2022

Sponsor
Protocol number

Clinical Study Report
Page x of y

14.3.6 Exposure, Safety Analysis Set

	CV7202 1 µg (N = xx)	CV7202 2 µg (N = xx)	CV7202 5 µg (N = xx)	Rabipur (N = xx)
Vaccination doses	1 xx (xx.x%)	xx (xx.x%)	xx (xx.x%)	xx (xx.x%)
	2 xx (xx.x%)	xx (xx.x%)		xx (xx.x%)
	3			xx (xx.x%)

PROGRAM SOURCE: tlf-###, DATA CUT OFF DATE: DDMMYYYY

RUN DATE: DDMMYYYY hh:mm

14.3.7.1 Weight and BMI, Safety Analysis Set

Parameter (unit)	Visit	CV7202	CV7202	CV7202	Rabipur
		1 µg (N = xx)	2 µg (N = xx)	5 µg (N = xx)	(N = xx)
Parameter (unit)					
Baseline					
n		xx	xx	xx	xx
Mean (SD)		xx.x (xx.xx)	xx.x (xx.xx)	xx.x (xx.xx)	xx.x (xx.xx)
Median		xx.x	xx.x	xx.x	xx.x
Min, Max		xx, xx	xx, xx	xx, xx	xx, xx
Actual result (Visit xx)					
n		xx	xx	xx	xx
Mean (SD)		xx.x (xx.xx)	xx.x (xx.xx)	xx.x (xx.xx)	xx.x (xx.xx)
Median		xx.x	xx.x	xx.x	xx.x
Min, Max		xx, xx	xx, xx	xx, xx	xx, xx
...					

PROGRAM SOURCE: tlf-###, DATA CUT OFF DATE: DDMMYYYY

RUN DATE: DDMMYYYY hh:mm

Programming note:

Display for parameters Weight and BMI and all visits with data collected for these parameters.

Number of decimals will vary by parameter - in general present mean, median to 1 decimal more than individual data, SD to 2 decimals more than individual data. Refer to SAP.

14.3.7.2 Vital Signs, Safety Analysis Set

Parameter (unit)	Visit	CV7202	CV7202	CV7202	Rabipur
		1 µg (N = xx)	2 µg (N = xx)	5 µg (N = xx)	(N = xx)
Parameter (unit)					
Baseline					
n		xx	xx	xx	xx
Mean (SD)		xx.x (xx.xx)	xx.x (xx.xx)	xx.x (xx.xx)	xx.x (xx.xx)
Median		xx.x	xx.x	xx.x	xx.x
Min, Max		xx, xx	xx, xx	xx, xx	xx, xx
Actual result (Visit xx)					
n		xx	xx	xx	xx
Mean (SD)		xx.x (xx.xx)	xx.x (xx.xx)	xx.x (xx.xx)	xx.x (xx.xx)
Median		xx.x	xx.x	xx.x	xx.x
Min, Max		xx, xx	xx, xx	xx, xx	xx, xx
...					

PROGRAM SOURCE: tlf-###, DATA CUT OFF DATE: DDMMYYYY

RUN DATE: DDMMYYYY hh:mm

Programming note:

Display for parameters systolic blood pressure, diastolic blood pressure, pulse and body temperature and all visits and timepoints with data collected for these parameters.

Number of decimals will vary by parameter - in general present mean, median to 1 decimal more than individual data, SD to 2 decimals more than individual data. Refer to SAP.

14.3.7.3.1 Hematology, Safety Analysis Set

Parameter (unit)	CV7202 1 µg (N = xx)	CV7202 2 µg (N = xx)	CV7202 5 µg (N = xx)	Rabipur (N = xx)
Parameter (unit)	Visit xx			
n	xx	xx	xx	xx
Mean (SD)	xx.x (xx.xx)	xx.x (xx.xx)	xx.x (xx.xx)	xx.x (xx.xx)
Median	xx.x	xx.x	xx.x	xx.x
Min, Max	xx, xx	xx, xx	xx, xx	xx, xx
Low	xx (xx.x%)	xx (xx.x%)	xx (xx.x%)	xx (xx.x%)
Normal	xx (xx.x%)	xx (xx.x%)	xx (xx.x%)	xx (xx.x%)
High	xx (xx.x%)	xx (xx.x%)	xx (xx.x%)	xx (xx.x%)
Visit xx	...			

Values are categorized into low-normal-high (below lower reference range/ within reference range/ above upper reference range). In the occurrence of a repeat, only the last valid result is considered.

Unscheduled visits are not presented for this summary. Results reported as below or above the detection limit are set to the detection limit.

PROGRAM SOURCE: tlf-###, DATA CUT OFF DATE: DDMMYYYY

RUN DATE: DDMMYYYY hh:mm

Programming note:

Display for all hematology parameters and all visits and timepoints with data collected for these parameters.

Number of decimals will vary by parameter - in general present mean, median to 1 decimal more than individual data, SD to 2 decimals more than individual data. Refer to SAP.

14.3.7.3.2 Biochemistry, Safety Analysis Set

Programming note:

Repeat table 14.3.7.3.1 for all biochemistry parameters.

Number of decimals will vary by parameter – in general present mean, median to 1 decimal more than individual data, SD to 2 decimals more than individual data. Refer to SAP.

Check whether footnote "Results reported as below or above the detection limit are set to the detection limit." Is applicable for this lab group and delete if not applicable.

14.3.7.3.3 Coagulation, Safety Analysis Set

Programming note:

Repeat table 14.3.7.3.1 for all coagulation parameters.

Number of decimals will vary by parameter - in general present mean, median to 1 decimal more than individual data, SD to 2 decimals more than individual data. Refer to SAP.

Check whether footnote "Results reported as below or above the detection limit are set to the detection limit." Is applicable for this lab group and delete if not applicable.

Appendix D2: Study-Specific Shells for Section 16.2

CureVac AG
CV-7202-104

Statistical Analysis Plan
24 February 2022

Sponsor
Protocol Number

Clinical Study Report
Page x of y

16.2.1.1 Subject Disposition
All Subjects

Group	Subject number	Complete subject code	Safety set [a]	FAS set [b]	Informed consent obtained on	(First) Vaccination on
-------	----------------	-----------------------	----------------	-------------	------------------------------	------------------------

[a] Received at least 1 administration of the trial product.

[b] Received at least 1 administration of the trial product and has baseline and at least 1 additional blood sample available for VNT analysis.

PROGRAM SOURCE: tlf-###, DATA CUT-OFF DATE: DDMMYYYY

RUN DATE: DDMMYYYY hh:mm

CureVac AG
CV-7202-104

Statistical Analysis Plan
24 February 2022

Sponsor
Protocol Number

Clinical Study Report
Page x of y

16.2.1.2 Discontinued Subjects
All Subjects

Group	Subject number	Complete subject code	Did the subject	Date of completion	Main reason for study	Comment
			complete the study?	or early termination	termination (Specification of other reason)	

PROGRAM SOURCE: tlf-###, DATA CUT-OFF DATE: DDMMYYYY

RUN DATE: DDMMYYYY hh:mm

Page 145/172

CONFIDENTIAL

CV-7202-104_Statistical_Analysis_Plan_V1.0.docm

CureVac AG
CV-7202-104

Statistical Analysis Plan
24 February 2022

Sponsor
Protocol Number

Clinical Study Report
Page x of y

16.2.2.1 Protocol Deviations
All Subjects

Group	Subject number	Complete subject code	Protocol Deviation Type Category	Description of Protocol Deviation
-------	----------------	-----------------------	----------------------------------	-----------------------------------

PROGRAM SOURCE: tlf-###, DATA CUT-OFF DATE: DDMMYYYY

RUN DATE: DDMMYYYY hh:mm

Page 146/172

CONFIDENTIAL

CV-7202-104_Statistical_Analysis_Plan_V1.0.docm

CureVac AG
CV-7202-104

Statistical Analysis Plan
24 February 2022

Sponsor
Protocol Number

Clinical Study Report
Page x of y

16.2.2.2 Eligibility and Subjects Not Fulfilling any Inclusion/Exclusion Criteria
All Subjects

Group	Subject number	Complete subject code	Enrolled/Screened under protocol version	Criterion NOT Met Criterion No.
-------	----------------	-----------------------	--	---------------------------------

PROGRAM SOURCE: tlf-###, DATA CUT-OFF DATE: DDMMYYYY

RUN DATE: DDMMYYYY hh:mm

Page 147/172

CONFIDENTIAL

CV-7202-104_Statistical_Analysis_Plan_V1.0.docm

CureVac AG
CV-7202-104

Statistical Analysis Plan
24 February 2022

Sponsor
Protocol Number

Clinical Study Report
Page x of y

16.2.3.1 Subjects Excluded from Analysis
All Subjects

Group	Subject number	Complete subject code	Excluded from FA set	Reason for exclusion
-------	----------------	-----------------------	----------------------	----------------------

PROGRAM SOURCE: tlf-###, DATA CUT-OFF DATE: DDMMYYYY

RUN DATE: DDMMYYYY hh:mm

Programming Note:

Subjects can have multiple reasons for being excluded from the analysis set (ie, not having postbaseline data by definition of the population or from having a major protocol deviation).

CONFIDENTIAL

CV-7202-104_Statistical_Analysis_Plan_V1.0.docm

CureVac AG
CV-7202-104

Statistical Analysis Plan
24 February 2022

Sponsor
Protocol Number

Clinical Study Report
Page x of y

**16.2.4.1 Demographics and Baseline Characteristics
Safety Analysis Set**

Group	Complete subject code	Age (years)	Gender	Childbearing potential	Ethnic origin	Height (cm)	Weight (kg)	BMI (kg/m ²)
-------	--------------------------	-------------	--------	------------------------	---------------	----------------	----------------	-----------------------------

*Programming Note:
Please display Gender as Female/Male, i.e. do not present the abbreviation F/M.*

PROGRAM SOURCE: tlf-###, DATA CUT-OFF DATE: DDMMYYYY

RUN DATE: DDMMYYYY hh:mm

CureVac AG
CV-7202-104

Statistical Analysis Plan
24 February 2022

Sponsor
Protocol Number

Clinical Study Report
Page x of y

**16.2.4.2 Medical History
Safety Analysis Set**

Group	Complete subject code	Diagnosis	Start date	Ongoing	End date
-------	--------------------------	-----------	------------	---------	----------

PROGRAM SOURCE: tlf-###, DATA CUT-OFF DATE: DDMMYYYY

RUN DATE: DDMMYYYY hh:mm

*Programming note:
Sort by start date within each subject.*

CureVac AG
CV-7202-104

Statistical Analysis Plan
24 February 2022

Sponsor
Protocol Number

Clinical Study Report
Page x of y

**16.2.4.3 Prior and Concomitant Medications/Vaccinations
Safety Analysis Set**

Group	Complete subject code	* Medication/Vaccination (PT)	Total daily dose	Unit/ Route/ Frequency	Start date/ Indication	Stop Date
-------	-----------------------------	----------------------------------	------------------	------------------------------	------------------------------	-----------

* P: prior, O: ongoing (starting pre-vaccination), C: concomitant (starting post-vaccination), PT: preferred term

PROGRAM SOURCE: tlf-###, DATA CUT-OFF DATE: DDMMYYYY

RUN DATE: DDMMYYYY hh:mm

*Programming note:
Sort by start date and stop date within each subject.*

CureVac AG
CV-7202-104

Statistical Analysis Plan
24 February 2022

Sponsor
Protocol Number

Clinical Study Report
Page x of y

**16.2.5 Vaccination Data
Safety Analysis Set**

Group	Complete subject code	Injection no.	Visit	Visit date	Has vaccine been administered?	Time of injection	Injection site	Description of site and reason	Comment
-------	-----------------------	---------------	-------	------------	--------------------------------	-------------------	----------------	--------------------------------	---------

PROGRAM SOURCE: tlf-###, DATA CUT-OFF DATE: DDMMYYYY

RUN DATE: DDMMYYYY hh:mm

CureVac AG
CV-7202-104

Statistical Analysis Plan
24 February 2022

Sponsor
Protocol Number

Clinical Study Report
Page x of y

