10.2 Populations for Analyses

Safety set: This is the subset of subjects, who have received at least one dose of the candidate rabies mRNA vaccine CV7202 or the active control Rabipur® and for whom any post-Day 1 safety data are available. The statement that a subject had no AEs (on the Adverse Event eCRF) constitutes a valid safety assessment. The analysis of safety will be performed on this population.

Full-analysis (FA) set: This is the subset of the Safety Set with subjects who have the baseline sample and at least one additional blood sample available for VNT analysis. This analysis set is the primary analysis set for all immunogenicity objectives.

Per protocol (PP) set: This is defined as a subset of the FA set as follows:

1. PP1 = Subjects enrolled in Group 1 (Rabipur®) and Groups 2 to 4 who have received at least 1 administration of the trial product (including those to be selected for the second vaccination), have completed the Day 57 visit and for whom baseline through Day 57 immunological results (at least rabies VNTs) are available.
2. PP2 = Defined as a subset of PP1 comprised of subjects who have received two administrations of the trial product, have completed the Day 91 visit and for whom baseline through Day 91 immunological results (at least rabies VNTs) are available.

Any subject for whom substantive protocol deviations are documented will be excluded from the PP set. The following pre-defined major protocol deviations will lead to the exclusion from the PP set:

- Any deviation of the Inclusion/Exclusion criteria.
- Any trial subject that requires therapy listed as an exclusion criterion in section 6.2.
- Any trial subject that has not received the trial product on the scheduled date.
- Any trial subject for whom the immunological sample has been taken outside of the planned visit window.
- Pre-existing RABV-G specific immune response.

Further subgroup analyses may be defined and specified in the statistical analysis plan (SAP).

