6.4 Interim Analysis and Data Monitoring

One or more interim analyses (IAs) may be performed for this trial. The data will be cleaned for all subjects. The analyses will be based on a data snapshot. Analyses will be performed on the safety set or subsets of it based on the availability of data. No decision-making is planned for the IAs and no adjustments for the trial are planned based on the results.

It is not planned to discuss any difference between the IAs and the final analysis in the clinical trial report.

A first interim analysis was performed after 16 subjects had been vaccinated (10 subjects in the CV7202 5 µg group and 6 subjects in the Rabipur group) and observed until Visit 8. The first interim analysis focused on safety aspects only. It was planned in a standalone interim analysis plan, which was finalized on 6 February 2019.

The second interim analysis was performed after 53 subjects had been vaccinated (16 subjects in the CV7202 1 µg group, 16 subjects in the CV7202 2 µg group, 10 subjects in the CV7202 5 µg group and 11 subjects in the Rabipur group) and observed until Visit 12 (Day 57). The second interim analysis focused on safety and immunogenicity. The analysis was primarily based on the interim analysis plan as of 06 February 2019 and subsequent change requests for tables.

For details of data monitoring please refer to section 4.

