8. ANALYSIS SETS

The following subject population will be used for safety analyses:

- **Safety analysis set** will include all subjects who have received at least 1 dose of the candidate rabies mRNA vaccine CV7202 or the active control Rabipur and for whom any post-Day 1 safety data are available. The statement that a subject had no AEs (on the Adverse Event eCRF) constitutes a valid safety assessment. The analysis of safety will be performed on this population.

The following subject populations will be used for analyses of immunogenicity objectives:

- **Full analysis (FA) set** is the subset of the safety analysis set with subjects who have the baseline sample and at least 1 additional blood sample available for VNT analysis. This analysis set is the primary analysis set for all immunogenicity objectives.

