9.2 Protocol Deviations

All potential protocol deviations will be assessed during a data review meeting. Protocol deviations due to missed or delayed assessments or in other relation to COVID-19 will be categorized as such.

The impact of protocol deviations on the analysis will be discussed during the data review meeting.

Subjects having protocol deviations and the specification of their protocol deviations will be listed including type of deviation.

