10. IMMUNOGENICITY ANALYSES

The immunogenicity analyses will be based on the FA set..

Details of analytical procedures, acceptance criteria, data analysis and reporting for immunogenicity data are described in the immunomonitoring analysis plan.

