12. CHANGES TO PROTOCOL-SPECIFIED ANALYSES

The protocol defines 2 PP sets as subsets of the FA set. Due to the small number of subjects per treatment group, it was decided that no per-protocol sets will be defined and used for analysis.

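### The note to SAP listing 16.2.3.1 gives a major protocol deviation as a reason for leaving the FA set, which contradicts every definition of that set

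*SAP*

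**What the plan says.** SAP 8 admits to the FA set those members of the safety analysis set who are "subjects who have the baseline sample and at least 1 additional blood sample available for VNT analysis". Protocol 10.2 uses the same condition: "subjects who have the baseline sample and at least one additional blood sample available for VNT analysis". Neither text contains a deviation criterion.

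On the role of the set, SAP 8 states: "This analysis set is the primary analysis set for all immunogenicity objectives". SAP 10 adds: "The immunogenicity analyses will be based on the FA set".

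Protocol 10.2 does list major deviations that lead to exclusion, but it ties them to the per-protocol (PP) sets. SAP 12 removes those sets because the groups are small: "it was decided that no per-protocol sets will be defined and used for analysis".

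On deviations in general, SAP 9.2 says: "The impact of protocol deviations on the analysis will be discussed during the data review meeting".

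Listing 16.2.3.1 has one set column, for exclusion from the FA set, and one column for the reason. Its programming note says that a subject may have several reasons and gives as examples "not having postbaseline data by definition of the population or from having a major protocol deviation".

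**The concern.** The note names a ground for exclusion that the definition does not contain. Because the listing has no other set column, the note cannot be read as referring to another population. A programmer or data review team acting on it would depart from SAP 8 without any change being declared in SAP 12.

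The VNT percentages, GMTs and their confidence intervals all rest on this one set. The trial is open label (Protocol 8.6). SAP 6.4 also describes, in the past tense, an interim analysis in 53 vaccinated subjects followed to Day 57: "The second interim analysis focused on safety and immunogenicity". A deviation-based exclusion could therefore be decided by people who already know some immunogenicity results. The SAP does not define a major deviation and does not say that FA membership is fixed before the data review meeting.

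**Working it through.** **Step 1: what each place says about FA membership.**

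| Place | Condition for membership | Deviation criterion? |
|---|---|---|
| Protocol synopsis and 10.2 | Safety set, baseline VNT sample, at least one more | No |
| SAP 8 | Same | No |
| Footnotes of tables 14.1.1 and 14.1.2 | Safety set, baseline and at least one postbaseline VNT sample | No |
| Footnote of listing 16.2.1.1 | At least one dose, baseline and at least one further VNT sample | No |
| Note to listing 16.2.3.1 | No postbaseline data, or a major deviation, as reasons for exclusion | **Yes** |

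Only the last row differs. Nothing else in either document supports it for the FA set. The protocol's list of major deviations belongs to the PP sets.

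**Step 2: what would be visible if the note were followed.** The exclusion would appear in the safety-set and FA counts of tables 14.1.1 and 14.1.2, in the flags of listing 16.2.1.1, and with its reason in listing 16.2.3.1. The titres would not appear in the planned VNT listing, because 16.2.6.1 is specified for the FA set. A reader could see that someone was removed but not what the removal did to the result.

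**Step 3: possible size.** The plan gives no figure to reproduce, and the documents report no response counts and no actual deviations. The counts below are assumptions: one non-responder per column. Column sizes come from the documents: 8 per regimen and 16 per dose in Groups 3 and 4, 10 in Group 2, and 11 Rabipur subjects vaccinated by the second interim analysis.

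The interval is the SAP's own exact Clopper-Pearson interval: lower limit = Beta quantile(0.025; x, n−x+1), upper limit = Beta quantile(0.975; x+1, n−x), with upper limit 100% when x = n. For example, the lower limit for 7/7 is 0.025^(1/7) = 0.590.

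| n | Before | One non-responder removed | One responder removed |
|---|---|---|---|
| 8 | 7/8 = 87.5% (47.3–99.7) | 7/7 = 100% (59.0–100) | 6/7 = 85.7% (42.1–99.6) |
| 10 | 9/10 = 90.0% (55.5–99.7) | 9/9 = 100% (66.4–100) | 8/9 = 88.9% (51.8–99.7) |
| 11 | 10/11 = 90.9% (58.7–99.8) | 10/10 = 100% (69.2–100) | 9/10 = 90.0% (55.5–99.7) |
| 16 | 15/16 = 93.8% (69.8–99.8) | 15/15 = 100% (78.2–100) | 14/15 = 93.3% (68.1–99.8) |

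Removing the non-responder raises the rate by 6.25 to 12.5 points. Removing a responder lowers it by 0.4 to 1.8 points. At an assumed 50% response, removing one non-responder raises it by 7.1 points at n = 8 (4/8 to 4/7) and 3.3 points at n = 16 (8/16 to 8/15).

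**Step 4: the GMT.** SAP 10.2 sets values below the quantification limit to 0.05 IU/ml. Suppose one subject has that value and the other n−1 all have titre g. Removing that subject multiplies the GMT by (g/0.05)^(1/n). With g from 0.5 to 5 IU/ml, the factor is 10^(1/8) = 1.33 to 100^(1/8) = 1.78 at n = 8, and 1.15 to 1.33 at n = 16. Removing one of the others instead multiplies it by (0.05/g)^(1/(n(n−1))), which at n = 8 is 10^(−1/56) = 0.96 to 100^(−1/56) = 0.92.

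**The case against.** The strongest reply is that this is a programming note on how to fill a reason column, not a rule of membership. The formal definition is in SAP 8, and the footnotes of 14.1.1, 14.1.2 and 16.2.1.1 repeat it. A programmer who follows those removes nobody for a deviation. SAP 12 points the same way: a sponsor that drops the PP sets because groups are small is unlikely to want the FA set trimmed. SAP 1 also requires departures from the plan to be documented in the trial report, and SAP 6 requires later analyses to be labelled post hoc.

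Most of this stands. It makes a leftover from the PP sets the likeliest explanation, though that is an inference. It does not remove the contradiction: the note is still an instruction in the approved shells, and someone who follows it departs from SAP 8.

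A reader might go further and infer that the FA set is in effect an undeclared per-protocol set, to be trimmed by people who have seen the results by group. The documents do not support that. SAP 6.4 does not say that interim immunogenicity results were shown by group. SAP 9.2 says only that the impact of deviations will be discussed; it gives no meeting date and no authority to change the sets. Nor could an exclusion be concealed, as step 2 of the working shows; only the excluded titres would be missing from the planned listing.

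**Conclusion.** The inconsistency is real and confined to one clause of one listing shell. Five other places define the FA set without a deviation criterion, and this note contradicts them. What follows is an opportunity for a deviation-based exclusion from the only immunogenicity set, not evidence that one is planned.

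The size depends wholly on assumed counts. With one non-responder in a column of 8, a single exclusion moves the rate up by 12.5 points or down by 1.8, depending on who is removed. The exact intervals before and after overlap heavily in either case.

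Severity is minor. Immunogenicity is secondary or exploratory and descriptive, no confirmatory inference is planned, and the primary safety endpoints use the safety set, which is not affected.

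**What to change.** In the programming note to listing 16.2.3.1, delete the second of the two reasons, the one naming a major protocol deviation, so that exclusion from the FA set follows SAP 8 alone. This costs one edit to a shell and removes no planned output.

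Optionally, add one sentence to SAP 9.2: protocol deviations do not change FA membership, and any analysis that omits subjects with deviations is a labelled sensitivity analysis shown beside the FA result. This is a useful clarification, but the contradiction is resolved without it.
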